16.5. Appendix 5: Data Display Standards & Handling Conventions

16.5.1. Reporting Process

Software	

 The currently supported versions of SAS software will be used. 	
Reporting Area	
HARP Server	: US1SALX00259
HARP Compound	: arprod\gsk2859716\mid205207\
Analysis Datasets	

 Analysis datasets will be created according to CDISC standards (SDTM IG Version 3.2 & ADaM IG Version 1.1). If the Study Data Standardization Plan (SDSP) exists for a study, ensure the CDISC versions are consistent. 	
Generation of RTF Files	

 RTF files will be generated for SAC deliverable. 	

16.5.2. Reporting Standards

General	

 The current GSK Integrated Data Standards Library (IDSL) will be applied for reporting, unless otherwise stated (IDSL Standards Location: https://spope.gsk.com/sites/IDSLLibrary/SitePages/Home.aspx): 
 4.03 to 4.23: General Principles 5.01 to 5.08: Principles Related to Data Listings 6.01 to 6.11: Principles Related to Summary Tables 7.01 to 7.13: Principles Related to Graphics Do not include subject level listings in the main body of the GSK Clinical Study Report. All subject level listings should be located in the modular appendices as ICH or non-ICH listings Note: All displays (TFL) will use the term 'Subjects' to reflect GSK Display Standards and CDISC SDTM/ADaM standards 	
Formats	

 GSK IDSL Statistical Principles (5.03 & 6.06.3) for decimal places (DP's) will be adopted for reporting of data based on the raw data collected, unless otherwise stated. Numeric data will be reported at the precision collected on the eCRF. 
 The reported precision from non eCRF sources will follow the IDSL statistical principles but may be adjusted to a clinically interpretable number of DP's. 	
Planned and Actual Time	

 Reporting for Tables, Figures and formal statistical analyses: 
 Planned time relative to dosing will be used in Figures, summaries, statistical analyses and calculation of any derived parameters, unless otherwise stated. The impact of any major deviation from the planned assessment times and/or scheduled visit days on the analyses and interpretation of the results will be assessed as appropriate. Reporting for Data Listings: 
 Planned and actual time relative to study drug dosing will be shown in listings (Refer to IDSL Statistical Principle 5.05.1). Unscheduled or unplanned readings will be presented within the subject's listings. 	

Unscheduled Visits	

 Unscheduled visits will not be included in summary Tables and/or Figures. 
 For by planned time analysis, unscheduled visits will not be included; For worst-case analysis, unscheduled visits will be included. All unscheduled visits will be included in listings. 	
Descriptive Summary Statistics	
Continuous Data	Refer to IDSL Statistical Principle 6.06.1
Categorical Data	N, n, frequency, %
Graphical Displays	

 Refer to IDSL Statistical Principals 7.01 to 7.13. 	

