8.5. Ocular Findings from Ophthalmic Exam (Part 2)

As outlined in study protocol (GSK Document Number.: [TMF-14344600](#)) Schedule of Activities (Table 7- Table 10 of Section 7), ophthalmic exams are scheduled at screening, during the study, end of treatment, and follow-up period. The ocular findings from ophthalmic exams will be analysed as described below.

1. From baseline to last follow-up, the following analysis will be performed:

a. Visual Acuity:

i. The best corrected visual acuity (BCVA) summary will be based on the Logarithm of the Minimum Angle of Resolution (logMAR score), where:

$$\text{logMAR score} = -\log_{10}(\text{Snellen Acuity Score})$$

The following categories of logMAR score changes from baseline are defined:

- No change/improved vision is defined as a change from baseline <0.12 ;
- A possible worsened vision is defined as a change from baseline ≥ 0.12 to <0.3 ;
- a definite worsened vision is defined as a change from baseline ≥ 0.3 logMAR score.

ii. A summary of characteristics of definite worsen vision as defined above by subject will be provided, including time to onset of first occurrence; outcome and duration of first occurrence; number of occurrences based on subjects with definite worsen vision; outcome post treatment exposure; time to resolution post-treatment exposure

iii. In addition, a summary of worst change from baseline (based on the eye with worst change) in BCVA score (logMAR score) will be provided for the following categories:

- Increase ≥ 0.12 to < 0.3
- Increase ≥ 0.3 to < 0.6
- Increase ≥ 0.6

iv. Number (%) of subjects with a decline in BCVA to 'light perception' (LP) or 'no light perception' (NLP) anytime post-baseline will also be provided.

b. Corneal Exam

i. Shift table from baseline to worst post-baseline by eye (R/L) and subject (worse eye, defined as the eye with the maximum worsening change from baseline) for corneal epithelium findings:

- Corneal epithelium (Normal to Abnormal), Corneal ulcer (No to Yes), Epithelial microcystic edema (No to Yes), Subepithelial haze (No to Yes), Corneal neovascularization (No to Yes), and Microcysts without edema (No to Yes)

- ii. For punctate keratopathy, summary Table of worst grade post-baseline and most frequent grade post-baseline across ocular exams by eye (R/L) and subject (worse eye)

- c. Lens

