3.0052	All Treated	See programming notes	Summary of Characteristics II of Worsening in Best Corrected Visual Acuity (BCVA) Score (logMAR Score)	
Report for: Part 1, Part 2, and combined Part 1 and Part 2; Summarize by: dose level (Refer to Section 5.1 for ordering of dose level and omit 1.92 mg/kg if data is not available) Total.; Refer to mid205678 (primary_07) Table 3.12060 for guidance.
 
Add the following footnotes:
 
[1] Duration is the time from onset of any visual acuity event (change from baseline logMAR score ≥ 0.3 in either eye) until the event is resolved (change from baseline logMAR score < 0.3 in both eyes). It requires at least a one day gap between the resolution of all events from first occurrence to the onset of second occurrence. [2] Snellen acuity response of "no equivalent value" will be set to a logMAR value of 1000 to indicate a worsening in result if there is a corresponding Non-Snellen acuity response. [3] If a subject has both a Snellen acuity and Non-Snellen acuity recorded at a visit, the Snellen acuity value will be selected. [4] The end of treatment exposure is defined as last infusion date +20 days.
	P-SAC [3], F-SAC [4]

Safety: Tables					
No.	Population	IDSL / Example Shell	Title	Programming Notes	Deliverable [Priority]
3.0053	All Treated	See programming notes	Summary of Findings for Punctate Keratopathy	
Report for: Part 1, Part 2, and combined Part 1 and Part 2; Summarize by dose level (refer to Section 5.1 for ordering of dose level and omit 1.92 mg/kg if data is not available; Total; Refer to mid205678 (internal_05) Table 3.0860 for guidance.
 
Add the following footnote:
 
Note: n reflects the number of eyes with punctate keratopathy worse than baseline at any post-baseline ocular exam.
	P-SAC [3], F-SAC [4]

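### The rule on unscheduled visits, as written, also takes unscheduled eye exams out of the vision-worsening onset, duration and recovery table, and nothing in the SAP puts them back

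*SAP*

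**What the plan says.** The Unscheduled Visits entry in SAP section 16.5.2 opens with an unqualified sentence: "Unscheduled visits will not be included in summary Tables and/or Figures". Two sub-bullets follow: "For by planned time analysis, unscheduled visits will not be included" and "For worst-case analysis, unscheduled visits will be included". A further bullet keeps everything in listings: "All unscheduled visits will be included in listings".

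Section 8.5 item 1.a.ii plans an event-type summary for visual acuity: "A summary of characteristics of definite worsen vision as defined above by subject will be provided, including time to onset of first occurrence". The item continues with outcome and duration of the first occurrence, the number of occurrences, and "outcome post treatment exposure; time to resolution post-treatment exposure". A definite worsening is a logMAR change from baseline of at least 0.3. Table 3.0052 (section 16.11.7) presents the summary at both the primary and the final analysis. Its first footnote begins "Duration is the time from onset of any visual acuity event"; the event is a change of at least 0.3 in either eye, and it resolves when both eyes are below 0.3.

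Item 1.a.iii is a separate summary of the worst change from baseline, based on the eye with the worst change. Two of its categories are 0.3 to below 0.6, and 0.6 or more.

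**The concern.** Section 16.5.2 names two kinds of analysis and gives each a rule. Table 3.0052 is of a third kind: it reports when a finding first appeared, how long it lasted, how often it recurred and when it resolved. It is a summary table, so the opening sentence covers it on its face, and the one exception does not.

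This matters because onset and recovery are what a reader takes from the table, and both depend on which exams are used. Ocular findings on ophthalmic exam are a Part 2 secondary safety endpoint (section 2.2), and corneal events and eye disorders are AESIs for belantamab mafodotin (section 8.2). If scheduled exams alone set the dates, onset and resolution move to later dates, and an episode seen only between scheduled exams does not appear.

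**Working it through.** The SAP gives no figure to reproduce. The check is textual, followed by a conditional bound.

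**Step 1. Which rule reaches which display**

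| Display | Type | Unscheduled exams under 16.5.2 as written |
|---|---|---|
| By-visit summaries | by planned time | excluded (first sub-bullet) |
| Worst change in BCVA, 8.5 item 1.a.iii | worst-case | included (second sub-bullet) |
| Listing 1.0057, visual acuity | listing | included |
| Table 3.0052, 8.5 item 1.a.ii | event-based summary | excluded by the opening sentence; named in neither sub-bullet |

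**Step 2. Does anything restore them for Table 3.0052?**

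- Section 8.5 covers baseline to last follow-up but does not mention unscheduled exams.
- The four footnotes to Table 3.0052 define duration, two points on Snellen and non-Snellen results, and the end of exposure. None mentions unscheduled exams.
- Section 16.3 applies no assessment windows, so an unscheduled exam is not slotted to a planned visit.
- The SAP is explicit elsewhere when it wants such data. Section 5.2 includes unscheduled visits in the baseline definition, and Tables 5 and 6 count progression found between scheduled visits at its assessment date. There is no matching sentence for post-baseline vision.

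Section 16.5.2 also says "Planned time relative to dosing will be used in Figures, summaries, statistical analyses and calculation of any derived parameters, unless otherwise stated". This carries little weight here: it concerns time relative to dosing and allows exceptions, and section 16.6.1 computes study day from the reference date itself.

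**Step 3. What follows if an unscheduled exam occurs and the opening sentence is applied**

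| Finding at the unscheduled exam | Table 3.0052 | Item 1.a.iii |
|---|---|---|
| First change of at least 0.3, still present at the next scheduled exam | counted, onset dated at the later exam | counted |
| First change of at least 0.3, below 0.3 at the next scheduled exam and not seen at any other scheduled exam | not counted | counted |
| Recovery to below 0.3, still recovered at the next scheduled exam | resolution dated at the later exam | not applicable |

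Late onset shortens the recorded duration and late resolution lengthens it, so the net error in duration can go either way.

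On the same set of exams, the subjects in Table 3.0052 (at least 0.3 in either eye) should equal the sum of the two upper categories of item 1.a.iii (at least 0.3 in the worse-changing eye), provided non-Snellen results are handled alike. If the two displays use different sets of exams, that equality can fail.

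**Step 4. Conditional bound on dating**

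The SAP does not state the exam interval L, so L is an assumption. An unscheduled exam k days after a scheduled one is followed by the next scheduled exam L − k days later, with k from 1 to L − 1. The largest delay is L − 1. If k is uniform, the mean delay is L/2.

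| Assumed L (days) | Largest delay, L − 1 | Mean delay, L/2 |
|---|---|---|
| 21 | 20 | 10.5 |
| 42 | 41 | 21 |
| 63 | 62 | 31.5 |

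These delays apply to an affected event only. They are not a bias in the table's summary statistics, which would also depend on how many events are affected. With about 28 Part 2 subjects (section 2.3), each subject not counted is 1/28 = 3.6 percentage points.

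**The case against.** The strongest reply is that the exclusion is one reading, not an established fact. Taken as absolute, the opening sentence contradicts its own second sub-bullet, so the sub-bullets may be meant as the whole rule. Table 3.0052 would then be unaddressed rather than excluded. That stands as a possible reading. It leaves the programmer with an unqualified opening sentence and no instruction for this table, so the same clarification is needed.

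Other signs point towards using all exams. Tables 5 and 6 date between-visit progression as found. The duration footnote separates occurrences by a one-day gap, which does little on a grid of scheduled exams alone. The table is also modelled on an output of another study that is not shown and may use every exam. These are fair inferences about intent, but the PFS and TTP rules do not govern visual acuity, and this SAP does not state the intent for Table 3.0052.

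It is also true that the finding would not vanish from the report. Worst-case summaries and the listing include it, AE-based eye tables use AE dates, and no hypothesis or stopping rule depends on Table 3.0052.

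A reader might go further in three ways, and the SAP supports none of them:

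- **That vision loss is missing or late, and that the two displays will disagree.** Both require that unscheduled exams occur and that the opening sentence is applied literally.
- **That such exams are prompted by symptoms, so that the loss of events is selective.** This is plausible, but no section says so.
- **That the OSDI deterioration and improvement summary (Table 6.003) has the same fault.** The SAP does not show that OSDI is collected at unscheduled visits.

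**Conclusion.** The point holds as a defect in a data-handling rule. As written, section 16.5.2 removes unscheduled eye exams from Table 3.0052; on the more generous reading it leaves the table without a rule. If such exams occur and are dropped, onset and resolution can be dated late, short episodes can go uncounted, and the subject count can fall below that of the worst-change summary at the same 0.3 threshold.

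The overall size is unknown: the SAP gives neither the exam interval nor the number of unscheduled exams. The delays in the working rest on assumed intervals and uniform exam timing, and apply per affected event. The reach is limited to one descriptive safety table in a single-arm study. The change should still be made, because the wording can be settled in the SAP at almost no cost.

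**What to change.** In section 16.5.2, replace the opening sentence and its sub-bullets with a rule that excludes unscheduled visits only from by-planned-visit summaries and includes them in worst-case analyses. Add that onset, duration, number of occurrences and resolution use all post-baseline exams, scheduled and unscheduled, at their actual dates. Repeat that last statement in the programming notes for Table 3.0052. Extend it to Table 6.003 only if OSDI is collected at unscheduled visits.

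The cost is a sentence or two in the SAP and a check that the program for Table 3.0052 follows it. The listing already calls for all unscheduled visits, so no new data are needed. No dose, exam schedule or clinical rule changes.

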16.5.3. Reporting Standards for Pharmacokinetic

Pharmacokinetic Concentration Data	
PC Windows Non-Linear (WNL) File	PC WNL file (CSV format) for the non-compartmental analysis by Clinical Pharmacology Modelling and Simulation function will be created according to SOP_314000: Non-Compartment Analysis of Clinical Pharmacokinetic Data [Note: Concentration values will be imputed as per GUI_51487
Descriptive Summary Statistics, Graphical Displays and Listings	Refer to IDSL PK Display Standards. Refer to IDSL Statistical Principle 6.06.1. Note: Concentration values will be imputed as per GUI_51487 for descriptive summary statistics/analysis and summarized graphical displays only.
NONMEM/Pop PK File	Pop-PK file (CSV format) for the POP-PK analysis by Clinical Pharmacology Modelling and Simulation function will be created according to the data specification detailed in Appendix 9 .
NONMEM/PK/PD File	Not applicable.
Pharmacokinetic Parameter Derivation	
PK Parameter to be Derived by Programmer	The following PK parameters will be derived by the Programmer: Ctrough (predose) and C-EOI at certain cycles. Note: C-EOI will not be designated as Cmax
Pharmacokinetic Parameter Data	
Is NQ impacted PK Parameters Rule Being Followed	Yes, refer to Standards for Handling NQ Impacted PK Parameters.
Descriptive Summary Statistics, Graphical Displays and Listings	Refer to IDSL PK Display Standards.]
Untransformed PK parameters	tmax (TMAX), tlast (TLST)

16.6. Appendix 6: Derived and Transformed Data

16.6.1. General

Multiple Measurements at One Analysis Time Point

 Mean of the measurements will be calculated and used in any derivation of summary statistics but if listed, all data will be presented. Participants having both High and Low values for Normal Ranges at any post-baseline visit for safety parameters will be counted in both the High and Low categories of “Any visit post-baseline” row of related summary Tables. This will also be applicable to relevant Potential Clinical Importance summary Tables.
Study Day

 Calculated as the number of days from First Dose Date: 
 Ref Date = Missing → Study Day = Missing Ref Date < First Dose Date → Study Day = Ref Date - First Dose Date Ref Date ≥ First Dose Date → Study Day = Ref Date - (First Dose Date) + 1
Change from Baseline

 Change from Baseline = Post-Baseline Visit Value - Baseline % Change from Baseline = $100 \times (\text{Post-Baseline Visit Value} - \text{Baseline}) / \text{Baseline}$ Maximum Increase/Decrease from Baseline = maximum (Increase/Decrease from Baseline) If either the Baseline or Post-Baseline Visit Value is missing, Change from Baseline and % Change from Baseline is set to missing
Date of Response

 For post-baseline disease assessments, the date of response (PR or better) is assigned to the latest date of disease assessments; for other response categories (MR, SD, NE, PD), the date of response is assigned to the earliest date of disease assessments.
Date of New Anti-Cancer Therapy

 Derived as the earliest date of new anti-cancer therapy, radiotherapy (where applicable) or cancer-related surgical procedure (where applicable) after date of study treatment discontinuation (date of last dose of study treatment). Missing or partial dates will be imputed for derivation of new anti-cancer therapy following rules specified in Section 16.7.2.1.

16.6.2. Study Population

Extent of Exposure

 ○ Missing treatment stop date will be imputed following rules specified in Section 16.7.2.1. ○ Combination Treatments ○ Extent of exposure will be calculated for each treatment component 
 ○ Non-Continual Drugs 
 ▪ Extent of exposure will be calculated based on treatment cycles derived based on cycle start dates in the exposure dataset ○ Duration of treatment will be calculated based on the formula: Duration on study treatment is calculated as the minimum of 
 ○ Maximum of (treatment stop date + lag time) – minimum of first treatment start date 
 ▪ for continual treatments, lag time = 1 ▪ for non-continual treatments, lag time = duration of one cycle ○ Data cut-off date – minimum of (first treatment start date) + 1 ○ Date of death – minimum of (first treatment start date) + 1 ○ Last contact date – minimum of (first treatment start date) + 1 (only applies for those lost to follow up/withdrew consent; does not apply for those who are still on study including follow-up) 
 ○ The last contact date is determined for each by selecting the latest date of all dates available in the database, and is derived as follows: 
 ▪ Date of death if the subject has died (DM.DTHDT). ▪ Else latest date from all other SDTM datasets. Partial and missing dates will not be imputed for the purpose of deriving date of last contact ○ The following dates below need to be removed from consideration. Note that if a participant has withdrawn consent from the study, then do not consider any dates in the database after the date of withdrawn consent. 
 ▪ DM.RFPENDTC, SV.SVENDTC, SV.SVSTDTC, SUPPAE.QNAM = "SASAEDTC", SUPPC1.QNAM="CMDSCRDT", SUPPCM.QNAM="CMDSCRDT". ▪ DS.DSSTDTC where DS.DSCAT="DISPOSITION EVENT" and DS.DSSCAT in ("STUDY CONCLUSION" ="STUDY TREATMENT DISCONTINUATION") and DS.DSDECOD not equal to "WITHDRAWAL BY SUBJECT" ○ Participants who were randomized but did not report a treatment start date will be categorized as having zero days of exposure ○ Dose intensity will be calculated based on the formula: 
 ○ Belantamab mafodotin: 
 ▪ Actual dose (mg/kg) = Actual dose of belantamab mafodotin (mg)/ Weight at baseline (kg) 
 • If the change of body weight is greater than 10%, the dose should be re-calculated based on the actual body weight on the day of dosing ▪ Cumulative Dose (mg/kg) = Sum of individual actual dose of belantamab mafodotin at all cycles ▪ Dose intensity (mg/kg/3 week) = Cumulative Dose/((last infusion date – first infusion date + 21)/21) ○ Pembrolizumab: 
 ▪ Actual dose (mg) = Actual dose of pembrolizumab (mg) ▪ Cumulative Dose (mg) = Sum of individual actual dose of pembrolizumab at all cycles ▪ Dose intensity (mg/3 week) = Cumulative Dose/((last infusion date – first infusion date + 21)/21)

Treatment Cycle

 Actual Treatment Cycle will be derived based on cycle start date in exposure data to distinguish from assessment cycle.
Actual Treatment

 Subject's actual treatment will be derived from exposure data. If a subject's actual treatment is the same as assigned treatment, actual treatment is the assigned treatment; if a subject received treatment different from assigned treatment for the entire duration of treatment, actual treatment is different from assigned treatment. 
 Refer to the adjustments due to body weight in Section 6.4.1 of protocol. If time is not available for at least one of the study treatments, then GSK2857916 will be selected over pembrolizumab.
Time since Initial Diagnosis

 Calculated as the number of Days from the Date of Initial Diagnosis: 
 First Dose Date = Missing → Elapse Time = Missing Date of Initial Diagnosis = Completely/partially Missing → Elapse Time = Missing Otherwise → Elapse Time = First Dose Date – Date of Initial Diagnosis + 1

16.6.3. Efficacy

Laboratory Parameters: Serum M-protein, Urine M-protein, Serum FLC

 If a laboratory value which is expected to have a numeric value for summary purposes, has a non-detectable level reported in the database, where the numeric value is missing, but typically a character value starting with '<x' or '>x' (or indicated as less than x or greater than x in the comment field) is present, the number of significant digits in the observed values will be used to determine how much to add or subtract in order to impute the corresponding numeric value. 
 Example 1: 2 Significant Digits = '< x ' becomes x – 0.01 Example 2: 1 Significant Digit = '> x' becomes x + 0.1 Example 3: 0 Significant Digits = '< x' becomes x – 1

16.6.4. Safety

Adverse Events
AE'S of Special Interest (belantamab mafodotin)

 Corneal events (GSK Scale): collected in eCRF Eye Disorders (CTCAE) Thrombocytopenia Infusion related reactions
AE'S of Special Interest (pembrolizumab)

 Overdose

Duration of AE

 Calculated as the number of days from AE Start Date to AE Stop Date: 
 AE Start Date = Missing → Elapse Time = Missing AE Stop Date = Missing → Elapse Time = Missing Otherwise → Elapsed Time = AE Stop Date – AE Start Date + 1
ECHO/MUGA

 Change from Baseline for cardiac data, e.g., Left Ventricular Ejection Fraction (LVEF), will be calculated based on the same modality (ECHO or MUGA) throughout the study for each subject. Post-baseline assessments with a different cardiac scan modality will not be used to calculate change from Baseline.

DLT
DLT Evaluable

 Participant is considered DLT evaluable if they fulfilled the 'All Treated' population criteria during part 1 (Dose Escalation) and are followed up for a 21-day period or withdrawn within 21 days due to an AE meeting the definition of a DLT as defined in Section 4.2.3.1 of protocol.

